3. STUDY DESIGN

One of the aims of this placebo-controlled, randomized, double-blinded study is to measure the efficacy of antiseptic mouthwashes on reducing SARS-CoV-2 cellular infectivity in COVID+ patient saliva (described above). Asymptomatic and symptomatic SARS-CoV-2+ subjects will be enrolled in the study (according to Inclusion and Exclusion Criteria - Section A.3). Symptomatic SARS-CoV-2+ subjects will be enrolled within 7 days of symptom onset. Subjects' samples are collected in the GoHealth Clinic (Adams School of Dentistry, UNC Chapel Hill, North Carolina, USA). Asymptomatic SARS-CoV-2+ subjects will be enrolled within one week of likely exposure. Study participants who meet all inclusion criteria without any exclusion criteria will be randomized to either an experimental or control group using block randomization.

Participants give a baseline salivary sample (2 mL over 5 min) and then asked to rinse with an mouth rinse for 30-60 sec (on-label instructions) according to the table below:

mouthrinse*	Number of final participants (sample size)	Group
1.5% w/v hydrogen peroxide rinse (Peroxyl)	25**	Experimental
0.12% Chlorhexidine Gluconate (Periogard)	25	Experimental

1 st Peroxyl; 2 nd Periogard [^]	25	Experimental
0.075% Cetylpyridinium Chloride (Colgate Total Zero)	25	Experimental
Sterile Water	25	Control

**All mouthrinses are commercially available in the USA, routinely used in clinical settings, and will be used in an on-label manner.*

***30 participants will be enrolled per regimen to ensure that complete data will be obtained from at least 25 participants per regimen. We assume that ≤ 5 enrollees will drop out or have incomplete data. 30 participants will be enrolled per arm to collect full data sets from 25 participants per arm, assuming some patients will need to be replaced due to inability to complete a visit (missing data).*

[^]For the sequential Peroxyl (1st) and Periogard (2nd) rinses, both oral rinses will be conducted in an on-label fashion. The patient will begin by rinsing with 10 mL of Peroxyl for 60 sec and then expectorate the mouthrinse into an empty tube. Then the patient will rinse with 15 mL of Periogard for 30 seconds and spit this mouthrinse into another empty tube.

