At the conclusion of sample collection, the participant will undergo a periodontal exam and will receive a \$50 gift card for their participation in visit 2. Study participation concludes following the periodontal exam after visit 2.

Missing data may occur due to participants being unable to complete a study visit due to health concerns or insufficient salivary production. Any missing data will be excluded from the study analysis. We do not anticipate that this will bias the data in any way. To accommodate this eventuality, we plan to enroll 30 participants per arm, to be able to have 25 participants per arm with full datasets.

All salivary samples will be collected on ice in sterile 50 mL conical vials and blood will be collected in EDTA-containing blood collection tubes. All collection tubes will be labelled “COVID Core” using pre-printed labels including the participants random alphanumeric study ID. Saliva samples will be cataloged and stored at the UNC Delta COVID Translational Initiative (also referred to as the COVID Core) for future RT-PCR, cytokine and chemokine concentration (Luminex) and viral infectivity assays. Samples will be transported on ice in a secondary container from the collection site to 4403A Koury Hall in leak proof biohazard bags. Samples will be processed according to the **sample processing and outcomes** procedure (below).

Participants who successfully provide salivary and blood samples and follow study protocols will receive a \$30 gift card as compensation at the end of visit 1 and \$50 at the end of visit 2. This study involves two, 90 minute on site visits.

During the period that the study participants are present in the clinic and giving saliva samples, we will monitor patient wellbeing and inquire about their comfort. If participants exhibit signs of distress or if oxygen saturation drops, research study staff will contact emergency medical responders to visit the patient and if deemed appropriate, the participants will be escorted to UNC hospital (adjacent building).

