6.2.5 Completion/Final Evaluation

This study requires two 90 minute visits. Participation is completed after the 2nd visit. For the second visit, participants will be scheduled to return to the GoHealth Clinical Research Unit at one week after the baseline assessment, during which additional salivary (1 time point, 2 mL of saliva over 5 min, no rinse will occur) and blood samples will be collected. At the conclusion of sample collection, the participant will undergo a periodontal exam and will receive a \$50 gift card for their participation in visit 2. Study participation concludes after visit 2 with no additional follow-up, as results are not relevant to the patient's clinical course and treatment management.

Subjects may withdraw from the trial at any time at their own request, or they may be withdrawn at any time at the discretion of the Investigator or Sponsor for safety, behavioral or administrative reasons.

The Investigator may discontinue a subject if, in the opinion of the Investigator, the subject is no longer a suitable candidate for the study. Possible reasons for the discontinuation of a subject are including but not limited to: adverse event, protocol deviation, insufficient saliva production, missed appointment, or subject no longer meets the eligibility criteria. The reason for discontinuation will be documented in the CDART record.

Patients may be removed from the study due to an allergic reaction to a mouth rinse or due to failure or inability to comply with study procedures.

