If a patient suffers from xerostomia/dry mouth, such that s/he cannot produce the baseline salivary sample volume or the immediate, 15 minute and 30 minute post-rinse saliva volumes, s/he will be removed from the study with a parking voucher, but without a visit 1 \$30 gift card and will be replaced. This would lead to missing data at the uncompleted time points. If a patient suffers from dry mouth, such that s/he cannot produce salivary sample volumes needed for later time points (45 min or 60 min post-rinse) but s/he produced sufficient baseline, immediate, 15 min and 30 min post-rinse samples, the participant will still be compensated with the visit 1 \$30 gift card and parking vouchers, and will remain in the study for visit 2 participation, if willing. At the conclusion of the visit 2 on site appointment (after saliva and blood samples have been collected and the periodontal exam is completed), participants will receive a \$50 gift card and parking vouchers. If a participant fails to carry out the at-home oral hygiene regimen with diary, cannot provide salivary or blood samples at visit 2, or cannot undergo the oral exam, they will not be provided the \$50 gift card for visit 2. Missing or deficient samples will be noted in CDART.

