9. INTERVENTION DISCONTINUATION

Subjects may withdraw from the trial at any time at their own request, or they may be withdrawn at any time at the discretion of the Investigator or Sponsor for safety, behavioral or administrative reasons.

The Investigator may discontinue a subject if, in the opinion of the Investigator, the subject is no longer a suitable candidate for the study. Possible reasons for the discontinuation of a subject are including but not limited to: adverse event, protocol deviation, insufficient saliva production, missed appointment, failure to comply with oral hygiene regimen, subject no longer meets the eligibility criteria. The reason for discontinuation will be documented in the patient's CDART record.

Patients may be removed from the study due to an allergic reaction to a mouth rinse or due to failure or inability to comply with study procedures. If a patient suffers from xerostomia/dry mouth, such that s/he cannot produce the baseline salivary sample volume or the immediate, 15 minute and 30 minute post-rinse saliva volumes, s/he will be removed from the study with a parking voucher, but without a visit 1 \$30 gift card and will be replaced. If a participant suffers from dry mouth, such that they cannot produce salivary sample volumes needed for later time points (45 min or 60 min post-rinse) but produced sufficient baseline, immediate, 15 min and 30 min post-rinse samples, s/he will still be compensated with the visit 1 \$30 gift card and parking vouchers, and will remain in the study for visit 2 participation, if willing.

At the conclusion of the visit 2 appointment (after saliva and blood samples have been collected and the periodontal exam is completed), participants will receive a \$50 gift card and parking vouchers. If a participant fails to carry out the at-home oral hygiene regimen with diary, cannot provide salivary or blood samples at visit 2, or cannot undergo the oral exam, s/he will not be provided the \$50 gift card for visit 2. Missing or deficient samples will be noted in CDART.

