11.3.3 Metrics

Every salivary sample will be collected in a conical tube with millimeter markings to monitor salivary volume. If insufficient saliva is collected, the study personnel collecting the samples from participants will note insufficient volume in the CDART database for each applicable time point and will indicate in CDART if the subject must be withdrawn and replaced. If a patient is unable to generate sufficient saliva for the 0 min, 15 min or 30 min post-rinse time points, the subject will be removed from the study and this will be noted in CDART along with their insufficient samples. If a subject is unable to generate sufficient saliva for time points 45 or 60 min post-rinse, the participant will remain in the study but their insufficient samples will be noted in CDART. If a patient is unable to tolerate the blood draws or periodontal exam, this will be noted in CDART and the patient will be withdrawn from the study.

For RT-PCR, viral infectivity and multiplex Luminex assays, all salivary samples will be run in triplicate with standard experimental controls (negative and positive) and protocol quality checks performed by research technical personnel in the COVID Core, [name], [name] and [name] laboratories. SARS-CoV-2 viral infectivity and RNA level will be measured using an *in vitro* infectivity assay (Reduction factor [RF] calculated from PFU / mL) and RT-PCR (relative quantification [RQ] ratio). Cytokine and chemokine concentration (pg/mL) will be measured using a prevalidated multiplexed quantitative analyte assay on a bioanalyzer (Luminex technologies). This objective provides urgently needed data to guide healthcare workers on the proper use of specific commercially available mouthwashes capable of reducing SARS-CoV-2 viral infectivity and potentially limiting COVID-19+ transmission.

Outcome assessments will be conducted weeks to months after the study visit, when RT-PCR, viral infectivity and cytokine/chemokine assays are conducted in the COVID Core and the laboratory of [name].

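### Data drop out on events after randomisation (failed saliva samples, the CT 22 cut-off, the visit 2 diary) with no defined analysis set and an unsupported no-bias statement

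*Combined protocol and SAP*

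**What the plan says.** **Missing data.** Section 3 attributes missing data to health concerns or too little saliva and then states: "Any missing data will be excluded from the study analysis. We do not anticipate that this will bias the data in any way". It plans 30 per arm so that 25 have complete data. A table footnote adds that "some patients will need to be replaced due to inability to complete a visit (missing data").

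**Removal after randomisation.** Section 6.2.2 confirms eligibility before assignment, and the rinse follows. Section 9 says that a participant who "cannot produce the baseline salivary sample volume or the immediate, 15 minute and 30 minute post-rinse saliva volumes, s/he will be removed from the study"; Sections 6.2.5 and 9 both add replacement. Section 6.2.5 comments: "This would lead to missing data at the uncompleted time points". Section 11.3.3 gives the trigger as insufficient saliva "for the 0 min, 15 min or 30 min post-rinse time points, the subject will be removed from the study", and staff "will indicate in CDART if the subject must be withdrawn and replaced". It also says: "If a patient is unable to tolerate the blood draws or periodontal exam, this will be noted in CDART and the patient will be withdrawn". Participants who fail only the 45 or 60 min sample stay in.

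**Analysis set.** Section 10.3 describes who is eligible. Neither it nor Section 10.6 says who is analysed, in which arm, or what becomes of samples from removed participants.

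**CT 22.** Sections 3 and 10.4 restrict the infectivity assay to samples with a cycle threshold of 22 or lower. Section 10.4 applies this to the 30 min post-rinse sample as well as to baseline.

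**Diary.** The Précis (Design and Outcomes) makes diary data, described as confirming compliance, a condition for including visit 2 secondary and tertiary data.

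**Safeguards present.** On discontinuation: "The reason for discontinuation will be documented in the CDART record". Saliva collectors and the assay technician are blinded (Section 6.2.3), and Section 10.6 plans general sensitivity analyses.

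**The concern.** Randomisation makes the arms comparable at entry. Each rule above decides whether data count by something that happens afterwards, so the analysed groups can differ from the randomised ones. The no-bias sentence would need loss to be unrelated to outcome, or related in the same way and to the same extent in every arm. The plan gives no ground for either, and the causes it names could relate to illness or to the rinse. The adverse-effect tables list dry mouth and salivary gland inflammation among reports for chlorhexidine. That does not show that a single rinse causes saliva failure, but it is a reason not to assume independence.

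The CT 22 rule bears directly on the primary outcome, because the sample that goes unassayed may be the one in which the rinse worked best. The diary rule can act differently by arm because, in the Précis, rinse arms follow a supplied regimen while controls keep their usual one.

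An undefined analysis set also leaves a choice that could be made after results are known.

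**Working it through.** **1. The plan's own figure.** Inputs from Section 3: 25 complete per arm, up to 5 of 30 lost. 25 / (1 − 5/30) = 30, so 30 per arm reproduces. (The Précis and Section 10.4 total of 125 equals 5 × 25, not 5 × 30 = 150. That is a separate matter; 30 per arm is used here.)

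**2. Complete-case or available-case?**
- Towards available-case: Section 3 excludes missing data, not participants; Section 6.2.5 places the gap at the uncompleted time points; those lacking only late samples are kept; Section 10.5 stores and analyses outcomes for each participant; Section 11.3.3 runs all saliva samples.
- Towards complete-case: the target of 25 complete records per arm, and removal with replacement.
- No sentence settles it.

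**3. Saliva loss if removed participants are left out.** The documents give no figure for how removed participants differ, so this is an assumption: they differ from retained ones by k SD of the outcome, with k from 0.5 to 1.0.

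Shift in the between-arm contrast = (m₁/30)k₁ − (m₂/30)k₂, where m is the number lost in each arm. With 25 per arm, SE = √(2/25) = 0.283 SD. With b = shift/SE, coverage of a nominal 95% interval = Φ(1.96 − b) − Φ(−1.96 − b).

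| Losses | k | Shift (SD) | b | Coverage |
|---|---|---|---|---|
| 5 v 5 | equal | 0 | 0 | 95% |
| excess 1 | 0.5 to 1.0 | 0.017 to 0.033 | 0.06 to 0.12 | 95.0% to 94.8% |
| excess 3 | 0.5 to 1.0 | 0.05 to 0.10 | 0.18 to 0.35 | 94.6% to 93.6% |
| 5 v 0 | 0.5 to 1.0 | 0.083 to 0.167 | 0.29 to 0.59 | 94.0% to 90.9% |
| 5 v 5 | 1.0 and 0 | 0.167 | 0.59 | 90.9% |

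The excess rows take the same k in both arms. For 5 v 0 with 25 and 30 analysed, SE = √(1/25 + 1/30) = 0.271, and coverage is 93.9% to 90.6%, the same to the nearest percent. The last row shows that equal numbers lost are not enough: the removed-versus-retained difference must also be equal.

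**4. CT 22.** The reduction factor is log10(pre/post). Take two participants whose pre-rinse samples are both at or below CT 22. If the post-rinse sample stays at or below 22, it is assayed and gives a reduction factor. If it rises above 22, there is no assay, and under the Section 3 rule no result. A rinse arm is then summarised over those whose RNA stayed high. If larger RNA falls go with larger infectivity falls, its effect is understated. The documents do not say how many samples would cross 22, so no size can be given, and step 3 sets no limit because these samples lie outside the allowance of 5. A pre-rinse sample above 22 is different: the rinse cannot cause it.

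**5. Conflicts to reconcile.** The sample-processing text in Section 3 and Section 11.3.3 put all samples through the infectivity assay; the CT 22 text does not. Sections 6.2.5 and 9 include baseline in the removal trigger and join the post-rinse samples with 'and'; Section 11.3.3 lists post-rinse samples only and uses 'or'.

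**The case against.** The best defence is that available-case analysis is the plainer reading of Sections 3 and 6.2.5, supported by Sections 10.5 and 11.3.3, and that the complete-data target only explains the enrolment buffer. A reader might infer that the plan commits to complete cases or discards samples from removed participants. The documents do not support that. What stands against the defence is that the plan never says so, and two competent analysts could analyse different people.

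The saliva-loss effect is also modest. Coverage falls to 91% only under an unfavourable combination, and the allowance of 5 includes visit 2 loss, which cannot affect visit 1 results. Someone removed at or before 30 min has no adequate 30 min sample, so a wider set recovers little of that infectivity endpoint. The main gain is from people withdrawn under Section 11.3.3 over the blood draw or periodontal exam, since both come after the visit 1 saliva series. For a single rinse loaded from the randomisation envelope, assigned and received arm should coincide, so analysis by assigned arm matters mostly at visit 2. All this is accepted.

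On CT 22, RT-PCR results remain for the unassayed samples, and a rinse that inactivates virus without lowering RNA would not trigger the rule. That limits the problem but does not remove it.

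The unmasked committee in Section 10.5 might suggest selective analysis. The same sentence has the statistician analyse first, so nothing of that kind is shown.

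**Conclusion.** The point holds as a gap in definition together with two selection rules, not as a demonstrated bias in the primary result. The no-bias sentence is unsupported and no analysis set is defined. The saliva-loss shift is 0.08 to 0.17 SD, with coverage about 94% to 91%, on the assumptions of a 0.5 to 1.0 SD difference and all 5 of 30 losses in one arm. It is near zero only if both the loss rate and the removed-versus-retained difference are equal across arms. The CT 22 rule combined with exclusion of missing data is the more direct threat to the infectivity outcome, and its size is unknown. The diary rule affects only visit 2 secondary and tertiary outcomes; whether a diary that shows non-compliance also excludes the participant is not stated. A reader might infer that the removal rules themselves are wrong. They are not judged here; the point is what happens to the data afterwards.

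**What to change.** 1. Define the primary set as all randomised participants in their assigned arm, using every result collected, including from those removed, withdrawn or replaced. State that the model uses all available time points. (Section 10, Primary Outcomes, names ANCOVA as primary and Section 10.6 names repeated measures as the main analysis; that is a separate point to reconcile.)
2. Reconcile the CT 22 rule with the text that has all samples assayed. If the rule stays, then where the pre-rinse sample is at or below CT 22, treat post-rinse samples not assayed because of CT as low (censored) infectivity, not as missing. Add a sensitivity analysis setting them to the assay's lower limit, which the plan must state, and to the pre-rinse value. Include opposite settings in the two compared arms, because the same setting in both does not bound a contrast. Report by arm how many have a pre-rinse sample above CT 22.
3. Analyse visit 2 outcomes by randomised arm whatever the diary status, with diary-compliant participants as a sensitivity analysis.
4. Report removals, replacements and missing results by arm with reasons from CDART, and delete the no-bias sentence.
5. Reconcile the differing statements of the removal trigger.

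Cost: protocol and SAP wording and minor analysis work. Reasons for loss are already recorded, and no extra participants, visits or procedures are needed.

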4. SELECTION AND ENROLLMENT OF PARTICIPANTS

4.1 Inclusion Criteria

Subjects must meet all of the following inclusion criteria to be eligible for enrollment in the study:

- Diagnosed SARS-CoV-2+ status. Either became symptomatic in the prior 7 days, or if not symptomatic, likely infected/exposed within the prior 7 days. All patients listed from the UNC Respiratory Diagnostic Center (RDC) have a confirmed SARS-CoV-2 infection and have consented to be contacted for research purposes. For patients contacting study coordinators for enrollment, who were not tested in the RDC, they must provide written proof of positive SARS-CoV-2 status in the prior 7 days.
- Individuals (all sex, all gender) at least 18 y.o.a. and at most 65 y.o.a. and in good oral health without any known allergies to commercial dental products or cosmetics. ASA class I or II prior to SARS-CoV-2 infection.
- Evidence of a personally signed and dated informed consent document indicating the subject (or legally acceptable representative) has been informed of all pertinent aspects of the trial and all of their questions have been answered.
- Able to comprehend and follow the requirements of the study (including availability on scheduled visit dates) based on research site personnel’s assessment.

- Females of childbearing potential will have a negative urine pregnancy test (on site) or be physically incapable of pregnancy (implants or injections, Intrauterine device, Bilateral tubal ligation, Hysterectomy, Ovariectomy, Women post-menopausal)

